4.2 Design Rationale

This study uses a placebo-control to estimate the effect relative to the placebo response that would occur due to the decrease of ticagrelor over time. The double-blind nature of the design will allow for unbiased safety assessment. The use of subjects pre-treated with ASA and ticagrelor allows for assessment of suppressed platelet function prior to study-drug treatment which is required to calculate reversal.

5 POPULATION

Approximately 200 male or female subjects between 50 and 80 years old who are in good general health or who have chronic, stable, and generally well-controlled medical conditions will be evaluated across centers in the United States (US) and Canada. The Sponsor reserves the right to include sites in other countries if deemed necessary.

If a subject is unable to comply with any of the study procedures before study drug dosing on Day 1, the subject's participation in the study will be re-evaluated by the Investigator in consultation with the Sponsor; the subject may not be eligible to participate in the study.

- 1. Subjects must be willing to remain at the study site at a minimum from Day 1 through Day 3 i.e. 48 hours following study drug dosing on Day 1
- 2. Subjects must be willing to return to the clinic for Follow-up visits on Day 7 and Day 35 ± 3

Note: If needed and at the discretion of the Investigator, a subject may remain in the study facility beyond the scheduled Day 3 discharge to accommodate Day 7 and Day 35 ± 3 follow-up visits

- 3. Subjects must refrain from smoking or using nicotine or nicotine-containing products and drinking alcohol-containing products, while confined to study site
- 4. Subjects must be willing to maintain their usual caloric intake and to consume only food and beverages provided by the clinical site while confined to the study site

Approximately 250-300 subjects may be screened to meet the target enrollment number of 200 subjects. Additional countries may be added at discretion of the Sponsor.

5.1 Definitions

Subjects officially enter the Screening Period following provision of signing an informed consent (written or verbal).

A screen failure is a consented subject who has been deemed ineligible based on 1 or more eligibility criteria or who has withdrawn consent prior to treatment assignment.

Screen failures may be rescreened upon confirmation with Sponsor. Screen failures may be rescreened once, upon review and confirmation from the Sponsor. For examples, subjects that have out of range laboratory results and vital sign measurements may have repeat assessment(s) during the Screening period.

An enrolled subject is one who has provided written or verbal informed consent.

A randomized subject is one who has been randomized to a treatment group on Day 1.

5.2 Inclusion Criteria

Subjects must meet all the following criteria prior to randomization:

- 1. The subject provides written or verbal informed consent (in-person or remotely as applicable and per local requirements) and agrees to comply with all protocol requirements throughout study participation
- 2. The subject is male or female between \geq 50 and \leq 80 years of age

- 3. The subject has a body mass index between 18 and 35 kg/m² and a weight of \geq 50 kg but \leq 120 kg, inclusive, on first day of screening
- 4. The subject is considered by the Investigator to be in good general health as determined by medical history, clinical laboratory test results, vital sign measurements, 12-lead ECG results, and physical examination findings at Screening and up to the time of randomization. Subjects with chronic, stable, and well-controlled medical conditions, are eligible provided they meet all other inclusion/exclusion criteria. Some examples of stable and well-controlled medical conditions include but are not limited to:
 - Hypertension controlled with no more than two antihypertensive drugs
 - Hyperlipidemia (defined with a Screening LDL of <190 mg/dL)
 - Diabetes controlled with diet/exercise or treated with no more than 2 medications and/or a Glycosylated Hemoglobin Hgb (HbA1c) ≤8%
 - Remote history of myocardial infarction (> 3 years prior to screening) with no symptoms
 - Mild hepatic enzyme elevation (AST or ALT <1.5 x upper limit of normal (ULN) or total bilirubin <1.2 x ULN)
- 5. Specific inclusionary laboratory values at Screening and Check-in require the following:
 - Stable white blood cell (WBC) count, platelet count, haemoglobin level with no clinically significant abnormality within the normal range as defined by the Investigator
 - Thyroid stimulating hormone (TSH) level within the normal range, as defined by the clinical laboratory at screening
 - Prothrombin time (PT) and/or international normalized ratio (INR) levels, plus partial thromboplastin time (PTT) and/or activated partial thromboplastin time (aPTT) level less than or equal to the upper limit of normal as defined by the clinical laboratory
- 6. Subjects taking medications for well-controlled medical conditions must have been on a stable dose (meaning no changes in dose) for at least 30 days prior to initiation of study drug
- 7. Subjects entering the study:
 - i. Who are not already taking daily aspirin must be willing to start an 81 mg daily dose of aspirin on Day -7 and must document daily dosing until the final dose is administered on the morning of Day 1
 - ii. Who are already taking daily aspirin must be willing to document a daily 81 mg dose between Day -7 and Day 1 and must suspend further aspirin dosing until discharge from the study on Day 3
- 8. Female subjects of childbearing potential must not be pregnant, lactating, or planning to become pregnant for 3 months after signing the informed consent, and have a negative serum pregnancy test at Screening and Check-in. Female subjects of childbearing potential must use 2 effective methods of birth control for 3 months after signing the informed consent

5.3 Exclusion Criteria

Subjects will be excluded from the study if they meet any of the following criteria:

- 1. In the opinion of the Investigator there are concern(s) regarding the ability of the subject to comply with study procedures and/or follow-up, or, if the subject is not suitable for entry into the study
- 2. History of any acute or chronic medical disorder expected to decrease the life expectancy of the subject to an extent where the subject's study participation is affected
- 3. Any clinically significant acute illness, medical/surgical procedure, or trauma within 4 weeks of the administration of study drug or any planned surgical procedure that will occur during the study (from Screening through the Day 35±3 follow up visit)
- 4. Any clinically significant abnormal findings in physical examination, vital signs, laboratory assessments, and ECG parameters identified during Screening or Check-in

Note: abnormal results may be repeated (locally or centrally) for confirmation immediately after the first out of range measurement. Abnormal vital signs may be repeated twice if needed, immediately after the first abnormal result and/or after the subject has rested for at least 10 minutes

- Specific vital sign exclusionary criteria occurring after 10 minutes of supine rest are any of the following:
- SBP <100 or >160 mm Hg
- DBP <40 or >95 mm Hg
- Resting HR <50 or >100 beats per minute (bpm)
- Specific exclusionary criteria for ECG parameters at Screening/Check-in or Day 1 are any of the following:
 - Prolonged Fridericia-corrected QT interval (QTcF) >450 milliseconds (msec), or pause >3 seconds, or family history of long QT syndrome
- 5. Any specific contraindication to ticagrelor as described in the Brilinta® prescribing information and as described below:
 - History of intracranial hemorrhage, active bleeding, or hypersensitivity or allergic reaction to ticagrelor or any component of the product
 - Any history of severe head trauma, intracranial neoplasm, arteriovenous malformation, aneurysm, or proliferative retinopathy
 - Any history of intraocular, retroperitoneal, or spinal bleeding
 - Having taken any oral or parenteral anticoagulant, including low molecular-weight heparin within 30 days of initiation of study drug
 - Severe hepatic impairment
 - Stool sample testing positive for occult blood within 3 months of Screening or at any time during the Screening period
- 6. Receiving chronic treatment with nonsteroidal anti-inflammatory drugs including aspirin (>100 mg daily), anticoagulants, or other antiplatelet agents that cannot be discontinued between the date the informed consent form was signed and the end of the study period

- 7. First positive test result for any hepatitis B (unvaccinated), hepatitis C, or human immunodeficiency virus types 1 or 2 antigen or antibodies at screening
- 8. Has received another investigational drug (defined as a small molecule or biologic compound which has not been approved for marketing) within 30 days of the administration of study drug in this study or within 5 half-lives of the experimental medication, whichever is longer
- 9. History of severe or ongoing allergy/hypersensitivity to any biologic therapeutic agent
- 10. Involvement with any PhaseBio or study site employee or their close relatives (e.g., spouse, parents, siblings, or children whether biological or legally adopted)
- 11. Previously received PB2452

5.4 Exceptions to Eligibility Criteria

Approval of protocol deviations to recruitment and enrollment criteria, also known as protocol waivers or exemptions, are not permitted.

6 STUDY CONDUCT

The Investigator will agree to perform all aspects of this study in accordance with the ethical principles that have their origin in the Declaration of Helsinki, ICH E6(R2): GCP, the protocol, and all national, state, and local laws or regulations.

This Phase 2B study will consist of:

- A Screening period (Days -45 to -4)
- Pretreatment with ASA 81mg daily (Day -7 to Day 1)
- Check-in Day–admission to study clinic (Day -3 to Day 3)
- Pretreatment and ticagrelor treatment (Day -2 to Day 1)
- On-site Randomization/Treatment (Day 1)
- 2-Day on-site Follow-up period (Day 1 to Day 3)
- Day 7 Follow-up visit (Day 7)
- Final Follow-up visit on (Day 35+3)

Plasma samples for PD and PK analysis of PB2452, ticagrelor and its active metabolite, (TAM) will be collected at Day -2, pre-dose (within 10 minutes prior to start of infusion), Day 1 and Day 2 at 5, 10 and 30 minutes and 1, 2, 4, 8, 12, 20, 24, 36, 48 hours following initiation of the study drug infusion. Plasma PK samples will also be collected on Day 7, and Day 35±3 after initiation of study drug infusion.

Safety and tolerability will be carefully monitored through the study. The existence of anti-drugantibodies will be assessed in all subjects at Day -3, Day 1 (randomization), Day 7 and 35 ± 3 following administration of study drug at 3 months and then every 6 months until return to baseline.

The estimated duration of the study for each subject, excluding screening, is approximately 35 ± 3 days.

6.1 Study Procedures

After signing the ICF, subjects will have study procedures at the time points specified in the Schedule of Events (Appendix 3).

Screening (Days -45 to -4)

- Subjects sign informed consent
- Inclusion/Exclusion criteria
- Demographics
- Medical history
- Urine drug screen
- Urine alcohol screen
- Serum pregnancy test for women of childbearing potential

- Serology tests
- Stool occult blood test
- Full physical examination, including height and weight
- Vital signs measured including SBP and DBP, body temperature, respiration rate (RR), and heart rate (HR)
- 12-lead Electrocardiogram (ECG)
- Clinical laboratory tests including hematology, chemistry, coagulation, and urinalysis
- Adverse Events (AEs)/serious adverse events (SAEs) collected
- Concomitant medications within -45 Days before subject provides informed consent. To include all prescription, over the counter (OTC) and supplements

Note: For subjects who are already taking aspirin they must be willing to document a daily 81 mg dose between Day -7 and Day 1 and must suspend further aspirin dosing from Day 1 until discharge from the clinical facility on Day 3

Screening (Day -7)

- Start ASA 81mg (enteric coated) daily (QD)
 - Subjects who enter the study already taking ASA 81 mg daily will document a daily ASA 81 mg dose)
- AEs/SAEs collected
- Concomitant medications

Screening (Day -6)

• ASA 81mg QD

Screening (Day -5)

• ASA 81mg QD

Screening (Day -4)

• ASA 81mg QD

Check-in/Pretreatment – Admission to Study Clinic - Baseline – Outpatient (Day -3)

- ASA 81mg QD
- Inclusion/Exclusion criteria
- Urine drug screen
- Urine alcohol screen
- Serum pregnancy test for women of childbearing potential
- Admission to study clinic
- Full physical examination and querying the subject for changes from baseline

- Vital signs measured including SBP and DBP, body temperature, RR, and HR
- Clinical laboratory tests including hematology, chemistry, coagulation, and urinalysis
- Serum immunogenicity
- AEs/SAEs collected
- Concomitant medications

Pretreatment - Baseline (Day -2) – May involve admission to study clinic as per study site's policy

- ASA 81mg QD
- Urine sample for PK ticagrelor/AR-C124910XX within 60 minutes prior to the first ticagrelor dose
- Ticagrelor administration
 - Single dose oral 180 mg (a.m.)
 - Single dose oral 90 mg 12 hours later (p.m.)
- Blood sampling for PK plasma (Plasma PB2452/Plasmaticagrelor/TAM/Unbound plasma ticagrelor/TAM) within 60 minutes prior to the first ticagrelor dosing
- Blood sampling for PD (PRU/VASP) within 60 minutes prior to the first ticagrelor dose
- AEs/SAEs collected
- Concomitant medications

Pretreatment - Baseline (Day -1) – May involve admission to study clinic as per study site's policy

- ASA 81mg QD
 - No less than 2 hours before study drug is started
- Inclusion/Exclusion criteria reconfirmed
- 12-lead ECG
- Local clinical laboratory tests including hematology, chemistry, coagulation, and urinalysis
- Ticagrelor administration
 - Single dose oral 90 mg (a.m.)
 - Single dose oral 90 mg (p.m.)
- Platelet biomarker sample collection (3.2% Na Citrate plasma tube)

Note: a single Qiagen PAXgene DNA tube per subject may be collected at any convenient sampling timepoint throughout the study

• AEs/SAEs collected

• Concomitant medications

In-House Treatment – Randomization (Day 1) – Admission to study clinic

- ASA 81mg QD
 - Approximately **2 hours prior** to study drug administration (PB2452/placebo)
- Vital signs measurements SBP, DBP, body temperature, RR, HR measured 30 to 60 minutes prior to initiation of study drug (PB2452/placebo) and at 15+5 minutes, 30+10 minutes, 45+10 minutes, 60+15 minutes and 24 hours±15 minutes, 48 hours±15 minutes hours following initiation of study drug infusion
- 12-lead ECG within **one hour before** study drug (PB2452/placebo), after bolus, (10 minutes), end of infusion (16 hours and 10 minutes) post initiation of the study drug (PB2452/placebo)
- Serum immunogenicity blood sample
- Ticagrelor administration
 - Single dose oral 90 mg (a.m.)
 - 2 hours+15 minutes prior to study drug administration (PB2452/placebo)
- Review of lab results of Day -1 and the vital sign assessments of Day 1 prior to randomization to confirm eligibility
- Randomization
- Administration of PB2452 or placebo at Hour 0
- Blood sampling for PK plasma (Plasma PB2452/Plasma ticagrelor/TAM/Unbound plasma ticagrelor/TAM) within 10 minutes prior to initiation of PB2452/placebo infusion (Hour 0), and 5, 10, 30 minutes, 1, 2, 4, 8, 12, 20, and 24 hours after initiation of study drug infusion
- Blood sampling for PD sampling (PRU/VASP) within 10 minutes prior to study drug (PB2452/placebo) infusion at hour 0 and at 5, 10, 30 minutes and 1, 2, 4, 8, 12, 20, and 24 hours after initiation of study drug (PB2452/placebo)
- Pooled urine sample for PK ticagrelor/AR-C124910XX at 0 to 6, 6 to 12 and 12 to 24 hours after the initiation of the study drug infusion
- Infusion site assessment to be done within 15 minutes prior to the initiation of the PB2452/placebo infusion at Hour 0 and at 1, 3, and 24 hours after initiation of PB2452/placebo infusion
- AEs/SAEs collected
- Concomitant medications (new medications and changes in dosing of previously reported medications)

In-House Treatment (Day 2)

- Vital signs measurements at 48 hours+15 minutes following initiation of study drug infusion as per Schedule of Events (Appendix 3)
- 12-lead ECG at 24 hours (±30 minutes) post initiation of study drug (PB2452/placebo) infusion
- Clinical laboratory tests including hematology, chemistry, coagulation, and urinalysis
- Blood sampling for PK plasma (Plasma PB2452/Plasma ticagrelor/TAM/Unbound plasma ticagrelor/TAM) 36 and 48 hours after initiation of study drug (PB2452/placebo)
- Blood sampling for PD sampling (PRU/VASP) 36 and 48 hours after initiation of study drug (PB2452/placebo)
- Pooled urine sample for PK ticagrelor/AR-C124910XX at 24 to 48 hours after the initiation of the study drug infusion
- Platelet biomarker sample collection (3.2% NaCitrate plasma tube)

Note: a single Qiagen PAXgene DNA tube per subject may be collected at any convenient sampling timepoint throughout the study

- Infusion site assessment at 48 hours after initiation of PB2452/placebo infusion
- AEs/SAEs collected
- Concomitant medications (new medications and changes in dosing of previously reported medications only)

In-House Treatment (Day 3)

- Brief physical examination and querying the subject for changes from baseline
- Vital signs measurements (SBP, DBP, RR and HR)
- Stool occult test (local or central laboratory) which may be completed on Day 2 if needed
- Blood sampling for PK plasma (Plasma PB2452/Plasmaticagrelor/TAM/Unbound plasma ticagrelor/TAM)
- Blood sampling for PD sampling (PRU/VASP) 48 hours after initiation of study drug (PB2452/placebo)
- Pooled urine sample for PK ticagrelor/AR-C124910XX at 24 to 48 hours after the initiation of the study drug infusion
- Infusion site assessment
- May repeat clinical laboratory tests (hematology, chemistry, coagulation, and urinalysis) if considered clinically significant by the Investigator based on Day 2 lab results
- AEs/SAEs collected
- Concomitant medications (new medications and changes in dosing of previously reported medications)
- Subjects discharged from study site/clinic

• If needed and at the discretion of the Investigator, a subject may remain in the study facility beyond the scheduled Day 3 discharge to accommodate Day 7 and Day 35±3 follow-up visits

Out-patient, Return to Study Site, Follow-up (Day 7) OR In-House if the Subject Remained at the Study Site until Day 7

- Brief physical examination and querying the subject for changes from baseline
- Vital signs measurements (SBP, DBP, RR, temperature and HR)
- 12-lead ECG
- Blood sampling for PK plasma (Plasma PB2452/Plasmaticagrelor/TAM/Unbound plasma ticagrelor/TAM)
- Platelet biomarker sample collection (3.2% Na Citrate plasma tube)

Note: a single Qiagen PAXgene DNA tube per subject may be collected at any convenient sampling timepoint throughout the study

- Serum immunogenicity
- Infusion site assessment
- Clinical laboratory tests including hematology, chemistry, coagulation, and urinalysis
- AEs/SAEs collected
- Concomitant medications (new medications and changes in dosing of previously reported medications only)

Out-patient, Return to Study Site, Follow-up, End of Study (Day 35±3) OR In-House if the Subject Remained at the Study Site until Day 35±3

- Serum pregnancy test for women of childbearing potential only
- Full physical examination, including height and weight
- Vital signs measurements (SBP, DBP, temperature, RR and HR)
- 12-lead ECG
- Clinical laboratory tests including hematology, chemistry, coagulation, and urinalysis
- Blood sampling for PK plasma (Plasma PB2452/Plasmaticagrelor/TAM/Unbound plasma ticagrelor/TAM)
- Platelet biomarker sample collection (3.2% Na Citrate plasma tube)

Note: a single Qiagen PAXgene DNA tube per subject may be collected at any convenient sampling timepoint throughout the study

- Serum immunogenicity
 - If anti-drug antibodies are detected, then a follow up visit 3 months post end of study (i.e. Day 35±3) is required. These samples are to be taken every 6 months until anti-drug antibodies no longer are present or until levels return to pre-dose state

- Infusion site assessment
- AEs/SAEs collected
- Concomitant medications (new medications and changes in dosing)

Out-patient, Return to Study Site, Follow-up, 3 months post EOS (Month 4) – If ADA Positive

- Serum immunogenicity
 - If anti-drug antibodies are detected at EOS visit, then a follow up visit 3 months post end of study (i.e. Day 35±3) must be collected

Out-patient, Return to Study Site, Follow-up, 6 months post last visit (Month 10) – If ADA Positive

- Serum immunogenicity
 - If anti-drug antibodies are detected at the follow up month 4 visit, blood samples are to be taken every 6 months until anti-drug antibodies are no longer present or until levels return to pre-dose state

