- k ASA 81 mg will be taken on Days -7, -6, -5, -4, -3, -2, -1, and on Day 1 no less than 2 hours before study drug is started. Subjects who enter the study already taking ASA daily must document a daily ASA 81 mg dose between Day -7 and Day -3. Subjects will receive daily ASA 81 mg between Day -3 (or Day -2 if the subject took ASA 81mg on Day -3 prior to Check-in) and Day 1 at the clinical facility and will suspend further ASA dosing until discharge from the clinical facility on Day 3
- Beginning in the morning on Day –2, a single dose of oral ticagrelor 180 mg will be given,
 followed by oral ticagrelor 90 mg every 12 hours (or BID) for 4 additional doses through to Day
 The final dose of ticagrelor should occur 2 hours±15 min before study drug is initiated)
- m PB2452/placebo will be administered at Hour 0 of Day 1

Infusion of PB2452/placebo is initiated on Hour 0 of Day 1 and will continue for approximately 16 hours for a total of 18 g (180 mL), as described in the protocol and pharmacy manual.

In subjects with known or reported concomitant use of moderate or strong CYP3A inhibitors (Appendix 4), an alternative 36 g (360 mL) regimen of PB2452 infused for approximately 24 hours will be administered as directed by the pharmacy manual

n A pre-ticagrelor blood sample will be collected on Day -2, within 60 mins prior to the dose of ticagrelor. Blood samples for determination of plasma PB2452, plasma ticagrelor/TAM and unbound plasma ticagrelor/TAM will be collected on Days 1 to 3 within 10 minutes prior to the initiation of PB2452/placebo infusion (Hour 0) and at 5, 10, 30 minutes and 1, 2, 4, 8, 12, 20, 24, 36, and 48 hours after initiation of study drug infusion

Plasma PK samples will also be collected on Day 7, and Day 35 ± 3 after initiation of study drug infusion

- Urine samples for PK ticagrelor/AR-C124910XX to be collected at i) 0 to 6 hours; ii) 6 to 12 hours and iii) 12 to 24 hours and iv) 24 to 48 hours after the initiation of the study drug infusion
- p Collection of Day -2 urine PK sample is a single sample collected within 60 minutes prior to the first ticagrelor dose

 g Blood samples for PD analysis (PRU/VASP testing) will be collected at the following timepoints: Day -2 and Day 1 (within 60 minutes prior to first ticagrelor dose) and Hour 0 (up to 10 minutes prior to PB2452/placebo infusion), 5, 10, 30 minutes, 1, 2, 4, 8, 12, 20, 24, 36 and 48 hours after initiation of PB2452/placebo infusion

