2.1.2.1 Administration Regimen

Approximately 200 subjects \geq 50 to \leq 80 years old will be administered aspirin 81 mg daily for at least 7 days prior to initiation of ticagrelor pretreatment with a 180 mg oral loading dose of ticagrelor, followed by 90 mg bid for a total of 5 doses of ticagrelor.

The peak plasma concentration of ticagrelor occurs approximately 2 hours after the last oral dose. Therefore, in this study, subjects will be randomized to receive PB2452 or placebo 2 hours after the 5th dose of ticagrelor to ensure that the initial assessment of reversal occurs at peak ticagrelor plasma concentrations.

PB2452 will be administered as a 16-hour and 10 minutes intravenous infusion in subjects who have been pretreated with a combination of oral ticagrelor plus low-dose aspirin (DAPT).

Dual antiplatelet therapy (DAPT) pretreatment includes oral doses of aspirin 81 mg will be administered daily for at least 7 days prior to study drug infusion and ticagrelor which will be administered as an initial 180 mg oral loading dose followed by 4 additional doses of 90 mg tablets prior to randomization.

PB2452/placebo infusion will be administered intravenously as follows starting at 2 hours after the final dose of ticagrelor:

- An initial 6 g bolus of PB2452 infused over 10 minutes followed immediately by an additional 6 g loading infusion of PB2452 over 4 hours
- A 6 g maintenance infusion of PB2452 administered over 12 hours will immediately follow completion of the loading regimen for a total infusion time of 16 hours and 10 minutes

If a subject is taking a moderate or strong CYP3A inhibitor, a 36 g alternative regimen of PB2452 will be administered intravenously starting at 2 hours after the final dose of ticagrelor:

- An initial 12 g bolus of PB2452 infused over 10 minutes followed immediately by an additional 12 g loading infusion of PB2452 over 6 hours
- A 12 g maintenance infusion of PB2452 administered over 18 hours will follow completion of the loading regimen for a total infusion time of 24 hours and 10 minutes

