4 STUDY PLAN

4.1 Study Design

This phase 2B study is a multi-center, randomized, double-blind, multicenter, placebo-controlled study. The study is designed to evaluate the efficacy of PB2452 in reversing the anti-platelet effects of ticagrelor as part of a dual antiplatelet regimen and to evaluate the safety and tolerability of PB2452 in subjects aged 50-80 years old.

Approximately 200 subjects between 50-80 years old will be enrolled in the US and other countries at the discretion of the Sponsor across 5-15 sites. The subjects will be randomized at a ratio of 3:1 receiving either the PB2452 investigational study drug or placebo. Hence, a total of approximately 150 subjects will be receiving PB2452 and approximately 50 subjects will be receiving placebo.

All subjects will be administered enteric coated aspirin 81 mg daily for at least 7 days prior to initiation of study drug for a total of 8 doses. Ticagrelor tablets will be administered prior to initiation of study drug with a 180 mg oral loading dose, followed by 90 mg bid for a total of 5 doses of ticagrelor. Two hours following the last dose of ticagrelor on morning of Day 1, subjects will receive either PB2452 or a placebo administered intravenously (IV) to assess reversal at peak ticagrelor plasma concentrations.

The infusion regimen is as follows:

- An initial intravenous (IV) bolus infusion consisting of a 6 g of study drug infused over 10 minutes followed immediately by an additional 6 g loading regimen of PB2452 infused over 4 hours
- A maintenance regimen of 6 g infused over 12 hours will immediately follow completion of the loading regimen for a total infusion time of approximately 16 hours

If a subject is taking a moderate or strong CYP3A inhibitor, a 36 g alternative regimen of PB2452 will be administered intravenously starting at 2 hours after the final dose of ticagrelor:

- An initial 12 g bolus of PB2452 infused over 10 minutes followed immediately by an additional 12 g loading infusion of PB2452 over 6 hours
- A 12 g maintenance infusion of PB2452 administered over 18 hours will immediately follow completion of the loading regimen for a total infusion time of 24 hours and 10 minutes

No interim analysis or subsequent long-term extensions are planned.

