- It has less than 3 data points;
- It has a positive slope (or correlation coefficient $[r]>0$);
- Adjusted $r^2 \leq 0.8$. (Adjusted $r^2 = 1 - \{(1-r^2) \times (n-1)\} / (n-2)$, where n is the number of data points in the regression and r^2 is the square of the correlation coefficient.).
- In cases where $C_t/\lambda z$ (i.e., the extrapolated portion of $AUC_{0-\infty}$) is $\geq 20\%$ of $AUC_{0-\infty}$, $AUC_{0-\infty}$ will be considered invalid.

Urine PK Concentration

Pooled urine samples to assess urine PB2452, ticagrelor and TAM concentrations will be collected over the following intervals: before dosing (within 60 minutes prior to the first ticagrelor dose on Day -2) and 0 to 6, 6 to 12, and 12 to 24 hours post dose.

For PB2452 concentration, urine concentration will be summarized by the time-intervals mentioned above. For Ticagrelor and TAM concentrations, the summary will be presented by treatment.

For each analyte, urine concentration and volume data will be listed by collection interval for each subject.

Urine Parameters

The urine PK parameters Ae_{24} , Ae_{48} , and Ae_{t1-t2} (for 0 to 6, 6 to 12, 12 to 24 and 24 to 48 hours), Fe_{48} , and CL_r for PB2452, ticagrelor and TAM in urine will be listed by subject and summarized for using descriptive statistics (number of subjects, mean, SD, CV, median, minimum, and maximum).

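### Section 6.1 gives the end-of-infusion ECG one clock time, 16 h 10 min, which does not fit the 36 g regimen, and the shared PK/PD schedule leaves 36 g subjects only two post-infusion draws by 48 h

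*Protocol*

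**What the plan says.** The protocol has two infusion regimens. The standard 18 g regimen is given "for a total infusion time of 16 hours and 10 minutes" (Section 2.1.2.1). Subjects on a moderate or strong CYP3A inhibitor receive 36 g with a "total infusion time of 24 hours and 10 minutes" (Section 4.1). Placebo is delivered on the same infusion schedule as the matching active regimen (Section 7.1.1.2).

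On ECGs, the Day 1 list in Section 6.1 includes one at "end of infusion (16 hours and 10 minutes) post initiation of the study drug", for all subjects. The ECG footnote to Table 1 and Appendix 3 lists an end-of-infusion ECG without a clock time. Section 6.1 opens by referring to Appendix 3 for the timing of procedures. Its Day 2 list adds a "12-lead ECG at 24 hours (±30 minutes) post initiation of study drug (PB2452/placebo) infusion". The next ECG in the protocol's schedule is on Day 7.

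On blood sampling, PRU/VASP draws after dosing are at "5, 10, 30 minutes, 1, 2, 4, 8, 12, 20, 24, 36 and 48 hours after initiation of PB2452/placebo infusion" (Section 1.1). Plasma PK uses the same times, plus Day 7 and Day 35. Neither schedule distinguishes the regimens.

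Duration of 80% and 100% response, by PRU and by PRI, is a secondary endpoint (Section 3.2.2). SAP Section 11 treats an elimination phase as invalid when "It has less than 3 data points". The SAP describes only the 16-hour regimen (Section 4.1).

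**The concern.** The only clock time that a site is given for the end-of-infusion ECG belongs to one of two regimens. For a 36 g subject, Section 6.1 and the Schedule of Events lead to tracings 8 h apart under one label. Sites could record different things in the same field, and a summary by time point would mix mid-infusion and end-of-infusion ECGs. Placebo subjects on the 36 g schedule are affected in the same way.

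The PK/PD schedule raises a separate measurement problem. Its 24 h draw comes just before a 36 g infusion ends, and the next is 12 h later. How long reversal lasts after the infusion, and how fast PB2452 is cleared, would be less well measured in the higher-dose regimen. The protocol's hypothesis (Section 9.1) concerns reversal that is sustained as well as rapid. The only earlier 36 g experience it describes is in volunteers aged 18 to 50 (Section 2.1.2.2), so 36 g data at ages 50 to 80 would be new.

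**Working it through.** **Infusion lengths.** The 18 g stages sum to 10 min + 4 h + 12 h = 16 h 10 min. The 36 g stages are "An initial 12 g bolus of PB2452 infused over 10 minutes followed immediately by an additional 12 g loading infusion of PB2452 over 6 hours" and "A 12 g maintenance infusion of PB2452 administered over 18 hours" (Section 4.1), which sum to 10 min + 6 h + 18 h = 24 h 10 min. Both agree with the stated totals.

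**ECG at 16 h 10 min in a 36 g subject.** Bolus and loading end at 6 h 10 min, so 10 h of the 18 h maintenance stage has run. Amount given = 12 + 12 + 12 × 10/18 = 30.7 g, and 30.7/36 = 85%. Time left = 24 h 10 min − 16 h 10 min = 8 h.

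**The 24 h ECG.** Its window is 23 h 30 min to 24 h 30 min. A 36 g infusion ends at 24 h 10 min, so 40 of the 60 minutes come before the end and 20 after it.

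**Post-infusion draws up to 48 h** (draw time minus end of infusion):

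| Draw | 18 g (ends 16 h 10 min) | 36 g (ends 24 h 10 min) |
|---|---|---|
| 20 h | 3 h 50 min | during infusion |
| 24 h | 7 h 50 min | 10 min before end |
| 36 h | 19 h 50 min | 11 h 50 min |
| 48 h | 31 h 50 min | 23 h 50 min |
| Number after end | 4 | 2 |

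**Offset of reversal.** Section 2.1.2.2 gives 20–24 h from the start for 18 g, which is 3 h 50 min to 7 h 50 min after the end. No offset time is given for 36 g. Assuming the same lag, 36 g offset is 24 h 10 min + 3 h 50 min = 28 h to 24 h 10 min + 7 h 50 min = 32 h. Any lag under 11 h 50 min falls between the 24 h and 36 h draws.

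**Washout.** The only PB2452 half-lives given are 1.5–9.2 h, from 0.1–1 g without ticagrelor (Section 2.1.4.1). Applying them to 36 g is an assumption. Fraction remaining = 2^(−t/half-life), with t counted from the end of infusion and Day 7 taken as 144 h:

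| Sample | t | Half-life 1.5 h | Half-life 9.2 h |
|---|---|---|---|
| 36 h | 11 h 50 min | 0.4% | 41% |
| 48 h | 23 h 50 min | 0.002% | 17% |
| Day 7 | 119 h 50 min | effectively 0 | 0.012% |

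Two draws by 48 h are below the SAP minimum of three. A third post-infusion point depends on a quantifiable Day 7 sample, at 0.012% or less of the end-of-infusion level. The documents give no assay limit for judging that.

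**The case against.** The strongest reply on the ECG is that Section 6.1 defers to Appendix 3, whose footnote is right for either regimen. A site following it takes the 36 g ECG at the true end. A reader might infer that every 36 g subject has a mid-infusion ECG recorded as end of infusion. The documents do not support that: the passages conflict, and the outcome depends on which one a site follows. Nor does it follow that no ECG is taken after a 36 g infusion before Day 7. The footnote calls for one at the end, and the 24 h window runs 20 minutes past it, although it does not guarantee a post-infusion tracing. A SAP Table 1 footnote mentions a Day 3 ECG, but the SAP cites the August 2019 protocol and version 2 schedules none.

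A reader might also infer that the whole schedule was built around 16 h 10 min. Only the ECG is tied to that time. The blood schedule has no 16 h draw, so 18 g subjects also lack an end-of-infusion sample.

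Nor is it established that offset and washout fall in the 24–36 h gap. Offset at 28–32 h is a projection from 18 g, and at the longest quoted half-life 41% of the drug remains at 36 h. Half-life, clearance and AUC to infinity are already conditional on the data allowing them. Cmax, AUC to 24 h and AUC to 48 h remain reportable, and pooled urine covers 24–48 h. A 12 h gap makes duration interval-censored, not unreportable.

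These replies limit the consequences. They do not remove the wrong clock time in Section 6.1 or the difference in post-infusion sampling.

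**Conclusion.** The point holds in two parts, of different certainty.

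- **ECG timing (high confidence).** For 36 g subjects Section 6.1 conflicts with the Schedule of Events footnote and the stated infusion length. The discrepancy is 8 h, at 85% of the dose. The 24 h ECG may fall before or after the infusion ends.
- **PK/PD sampling (the gap is certain, its effect less so).** There are two post-infusion draws by 48 h against four, and none between 24 h and 36 h. If 36 g offset follows the 18 g lag, duration of response is known only to within 12 h. PB2452 half-life, clearance and AUC to infinity may fail the three-point rule unless Day 7 is quantifiable. This rests on the assumed lag and on half-lives from much lower doses.

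The primary endpoint, confined to the first 4 h, is unaffected. Section 2.1.2.2 states the aim in terms of the 18 g regimen. The number of 36 g subjects is not stated, though enrolment is plausible: controlled hypertension is eligible (Section 5.2), and diltiazem and verapamil are listed inhibitors (Appendix 4). The correction is worth making because it is cheap.

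**What to change.** 1. Reconcile the Section 6.1 Day 1 list, the ECG footnotes in Table 1 and Appendix 3, and the infusion lengths in Section 4.1, so that an ECG recorded as end of infusion refers to the regimen actually given, active or matching placebo.
2. Have the sponsor reconcile the 24 h safety assessments (ECG and infusion-site check) with the 36 g infusion end, and state whether they are meant to come before or after it. That timing is for the sponsor to decide.
3. For measurement only, place one of the existing 36 g PK/PD draws between 24 h and 36 h, for active and placebo alike. Post-infusion draws by 48 h rise from two to three, and the total is unchanged. Subjects are already on site to 48 h.
4. State in the SAP how response duration and terminal-phase parameters will be handled for 36 g subjects.

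The cost is schedule wording, a regimen-specific visit form and one fewer mid-infusion reading. If the 20 h draw is the one moved, a 12–24 h gap opens during maintenance, when sustained reversal is also of interest. Three draws do not guarantee three quantifiable values: at a 1.5 h half-life only 0.4% remains by 36 h. Matching the 18 g lags in full would take draws at both 28 h and 32 h.
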